4.5 Treatment Compliance of Study Product

The overall treatment compliance of study product in the treatment period is calculated as: $100 \times$ The total number of doses / (The total number of days of exposure to study product × 6), where the total number of doses is summed from numbers of daily doses recorded on the Study Product Diary. Overall compliance in the treatment period is categorized as <80%, 80-120%, >120%.

5 ANALYSIS OF EFFICACY

5.1 Primary Efficacy Variable

The primary efficacy variable is the achievement of epithelial healing at Visit 6/Week 8, which is defined as Grade 1 or absence of staining (Grade 0) in the central qualifying zone of study eye via FCS (per NEI scale). The primary efficacy variable will be summarized as a binary goal attainment variable (Yes/No).

The primary analysis will be based on observed cases (i.e. no missing data imputation). As a sensitivity analysis, the last post baseline observation prior to Week 8 will be carried forward for imputing missing data at Week 8. In addition the worst post baseline observation prior to Week 8 will be carried forward for imputing missing data at Week 8 and patients who took any rescue medication prior to Week 8 will be considered as a treatment failure (not epithelial healed) at Week 8.

All summaries and analyses for the primary efficacy variable will be presented for both FAS and FTS populations.

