carton. Patients should be instructed to try and complete therapy before last treatment appointment, so at time of end of treatment evaluation the patient should have completed the six times a day dosing on Day 56/Week 8 for Visit 6. This will require PIs and their staff to try and schedule the last visit at the end of the day, so the patient has sufficient time to complete 6 doses on the day of Visit 6.

- 6.1.6. Visit 6 (Day 56/Week 8 4 days): END OF TREATMENT OR PREMATURE DISCONTINUATION VISIT
 - 1. IDEEL
 - 2. EQ-5D-5L
 - 3. *Pregnancy Test for women of childbearing potential: Perform a urine pregnancy test and record the results
 - 4. *Concomitant Ocular and Systemic Medications Update
 - 5. *Record AE's
 - **6. Ophthalmic Examinations:** The following examination/procedures will be performed on BOTH EYES unless otherwise specified:
 - a. BCDVA
 - b. External Ocular Examination
 - c. Slit Lamp Examination
 - d. Corneal Photo Without Fluorescein
 - e. Instill Fluorescein
 - f. TFBUT
 - g. Corneal Fluorescein Staining
 - h. Corneal Photo with Fluorescein
 - i. Wait 10 minutes before performing Schirmer Test
 - j. Corneal Sensitivity
 - k. Schirmer Test Without Anesthesia (Schirmer I)
 - l. IOP
 - m. Anterior Segment OCT (selected sites)

- n. Confocal Microscopy (selected sites)
- 7. Collect used Study Product and Subject Dosing Diary
- 8. Dispense Daily Study Dosing Diary
- 9. Dispense Systane®
- 6.1.7. Visit 7 (Day 224/Week 32 ±7 days): FOLLOW-UP/FINAL STUDY VISIT
 - 1. IDEEL
 - 2. EQ-5D-5L
 - 3. *Concomitant Ocular and Systemic Medications Update
 - 4. *Record AE's
 - **5. Ophthalmic Examinations**. The following examination/procedures will be performed on BOTH EYES unless otherwise specified:
 - a. BCDVA
 - b. External Ocular Examination
 - c. Slit Lamp Examination
 - d. Corneal Photo Without Fluorescein
 - e. Instill Fluorescein
 - f. TFBUT
 - g. Corneal Fluorescein Staining
 - h. Corneal Photo with Fluorescein
 - i. Wait 10 minutes before performing Schirmer Test
 - j. Corneal Sensitivity
 - k. Schirmer Test Without Anesthesia (Schirmer I)
 - l. IOP
 - m. Anterior Segment OCT (selected sites)
 - n. Confocal Microscopy (selected sites)

- 6. *Collect Daily Study Dosing Diary
- 7. Patient will be discharged from the study

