6.2. EARLY WITHDRAWAL FROM STUDY

A premature discontinuation will occur when a patient who signed the ICF ceases participation in the study, regardless of circumstances, before the completion of the study protocol procedures. Patients can be prematurely discontinued from the study for one of the following reasons:

- Progression from Stage 1 to Stage 2 or Stage 3 NK, or corneal melting/perforation
- At the PI discretion patient is considered to be a non-responder (no improvement from baseline).
- In the qualifying/Study Eye, the FCS is unchanged (Grade=3) from baseline after 8 weeks of treatment in the qualifying NEI zone or there is an increase in FCS ≥1 within a non-qualifying NEI zone in the same eye.
- Decrease in BCDVA by >10 ETDRS letters
- Onset of infection (bacterial or viral)
- Protocol violation, including lack of compliance defined as <80% of doses taken based on diary documentation between treatment clinic visits.
- Withdrawal of consent
- Lost to follow-up during the treatment period (Every effort must be made to contact the patient; a registered letter must be sent)
- Study terminated by the Sponsor
- Other reasons, such as administrative reasons or pregnancy
- Development of AE or unacceptable toxicity per the investigator's discretion, precluding further therapy with the study drug.
- Severe protocol violations, such as an incorrect treatment administration, or a concomitant use of not permitted medications. Before removal, these cases should first be discussed with Dompé.

The reasons for premature discontinuation from the study will be reflected on the Study Termination Record of the CRF. For patients who prematurely discontinue, Visit 6 procedures will be completed, and these patients will be considered off study and will no longer be followed.

For patients that discontinue prematurely, the investigator should refer patients for further treatment as appropriate.

Replacement Procedures

Patients in this study who prematurely discontinue before completion of 8 weeks of treatment with OxervateTM will be replaced. Patients prematurely discontinuing during follow up treatment will not be replaced.

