1.2 Study Design

This clinical study will be a multi-center, open label, prospective study of 8 weeks of treatment with 24 weeks of follow-up to evaluate the safety and efficacy of OXERVATE $^{\text{TM}}$ 0.002% (20 mcg/mL) cenegermin-bkbj ophthalmic solution administered as one drop in the affected eye(s), 6 times per day at 2-hour intervals, for eight weeks in patients with Stage 1 NK. The study population will comprise of both female and male subjects. A total of 35 evaluable subjects (those patients completing 8 weeks of Oxervate $^{\text{TM}}$) aged \geq 18 years will be enrolled in approximately 5 sites within the United States.

All patients will attend the following clinic visits in the following sequence:

- Screening (Visit 1/Day -14)
- Baseline and First Study Product Pick-Up (Visit 2/Day 0)

- Product Pick-Up (Visit 3/Week 2)
- Treatment Assessment and Study Product Pick-Up (Visit 4/Week 4)
- Product Pick-Up (Visit 5/Week 6)
- End of 8-week Treatment (Visit 6/Week 8)
- Follow-Up and Final Study Visit (Visit 7/Week 32)

The trial structure for subjects is shown in Figure 1.

The study will be a total of 34 weeks in duration: a screening (washout) period of 2 weeks, followed by 8 weeks of treatment and a 24-week follow-up period. At the end of the screening period (at Visit 2), patients meeting the entry criteria for this study will be assigned to treatment with OXERVATE[™] 0.002% (20 mcg/mL) cenegermin-bkbj ophthalmic solution which will be known as Study Product beginning the morning following Visit 2. On Day 0 (baseline visit-Visit 2) and at Visit 3, Visit 4, and Visit 5, the study personnel will give to the Subject the b-weekly kit containing 2 weeks of the study product and delivery kits.

Following the completion of the treatment period, patients will be followed up for an additional 24 weeks (for patients healed and non-healed [and not meeting discontinuation criteria] at Week 8) and will be evaluated at the end of the followup period. At the investigator's discretion, the subject may be seen for an Unscheduled Visit to evaluate for safety. Patients who prematurely discontinue for whatever reason will not be followed post discontinuation and should have Visit 6 assessments completed.

Ocular assessments should be conducted by the same assessor throughout a subject's participation period to reduce observer variability. All efficacy

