1.3.3 Efficacy Assessments

1.3.3.1 Fluorescein corneal staining

Following the instillation of fluorescein in the qualifying eye(s) grade (density) of the SPK will be determined at Visit 1, 2, 4, 6, 7 using the NEI (National Eye Institute [NEI]/Industry Workshop 0-15) scale of 0 to 3 for each of the five areas: Zone 1 Central, Zone 2 Superior, Zone 3 Temporal, Zone 4 Nasal, and Zone 5 Inferior.

Epithelial healing, defined as Grade 1 or absence of staining (Grade 0) in a previously qualifying zone, will be determined by the investigators and recorded on eCRF at Visit 4, 6, and 7.

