2.5 Out of Window and Unscheduled Visits

All scheduled assessments after first administration of randomized study product will be used. The protocol defined windows for scheduled visits will not be used in the analyses by visit. Data will be assigned to the scheduled visit closer in time to the scheduled visit. Unscheduled visit data will only be used in an analysis if there is no other available data closer in time to a scheduled visit. Post first dose unscheduled assessments will be taken into account for worst-case determination as applicable. All unscheduled visit data will be included in data listings.

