2.11 Handling of Missing Data

The primary efficacy analysis will be based on observed cases (i.e. no missing data imputation). Sensitivity analyses will be performed using various missing data imputation approaches as described in Section 5.1.

All analyses unless specified will be conducted on an as observed case basis, that is, no further imputation of missing data will be carried out unless expressly stated otherwise.

Imputation for Missing Concomitant Medication and AE Start and Stop Days:

Missing and/or incomplete dates for concomitant medications and AEs will be imputed for calculating Start/Onset Day and Stop Day only. The Start/Onset Day

and Stop Day may be used for calculating prior or concomitant medications or calculating treatment emergent AEs. Missing and/or incomplete dates will be imputed in a manner that assumes the worst case scenario (i.e. Start/Onset as close as possible to the First Study Treatment Administration and stopped such that it assumed to have lasted for the longest possible duration, taking into account that the Start/Onset date should not be after the Stop date).

Imputation for missing Stop Date:

- For a completely missing stop year (regardless of day or month) the medication/AE will be assumed to be ongoing.
- For a missing stop month (and a medication/AE that is not 'Ongoing') the medication/AE will be assumed to have ended the last available month of that year.
- For a missing stop day (and a medication/AE that is not 'Ongoing') the medication/AE will be assumed to have ended on the last day of the month if the month is available.

Imputation for missing Start/Onset Date:

- For a completely missing Start/Onset date (day, month and year), the Start Day of medication/AE will be considered pre-treatment (i.e. prior) if the stop date or partial stop date concludes the medication/AE was stopped before the first administration of the study product. In all other instances (i.e. inconclusive stop date or Ongoing medication/AE) the Start Day of medication/AE will be assumed to have started at the date of the first administration of the study product (i.e. assumed to be concomitant or treatment emergent as is applicable).
- For a missing start/onset month the medication/AE will be assumed to have started in January of that year, or at the date of first administration of the study product if the start/onset year was the same as the year of first administration of the study product.

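### The primary Week 8 healing rate is observed-case with no rule counting early stops for progression or non-response as not healed, and SAP 2.5 can move their exit staining grade away from Week 8

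*SAP*

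**What the plan says.** - **Missing data.** SAP 5.1 says "The primary analysis will be based on observed cases (i.e. no missing data imputation" and SAP 2.11 repeats it: "The primary efficacy analysis will be based on observed cases (i.e. no missing data imputation". The endpoint is Grade 0 or 1 in the central zone of the study eye at Visit 6/Week 8, reported for the FAS (all enrolled patients with at least one dose) and the full treated set (FTS).
- **Early stops.** Protocol 6.2 lists among the reasons "Progression from Stage 1 to Stage 2 or Stage 3 NK, or corneal melting/perforation" and, separately, non-response at the investigator's discretion. It sets no minimum time on treatment for either. Patients who stop before completing 8 weeks are replaced.
- **Exit visit.** Protocol 6.1.6 titles Visit 6 "END OF TREATMENT OR PREMATURE DISCONTINUATION VISIT". SAP 1.2 adds: "Patients who prematurely discontinue for whatever reason will not be followed post discontinuation and should have Visit 6 assessments completed". Under SAP 1.3.3.1, epithelial healing "will be determined by the investigators and recorded on eCRF at Visit 4, 6, and 7".
- **Visit assignment.** SAP 2.5 says that scheduled assessments will be used, then "The protocol defined windows for scheduled visits will not be used in the analyses by visit" and "Data will be assigned to the scheduled visit closer in time to the scheduled visit". It does not mention the premature-discontinuation visit.
- **Sensitivity analyses.** SAP 5.1 plans last-observation (LOCF) and worst-observation (WOCF) analyses, tabulated on the FAS. The only failure rule concerns rescue use and appears alongside the WOCF analysis.

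**The concern.** A patient withdrawn because the cornea progressed or did not respond has shown the outcome that the endpoint is meant to capture. An observed-case rate is safe for such a patient only if a Week 8 value exists. The plan leaves that open: the visit label says the exit FCS is Visit 6, while the timing rule, applied literally, can make it Week 4. Two programmers could both follow the SAP and report different primary rates.

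If the timing rule is applied, failures leave the denominator while replacements keep enrolment going until 35 patients complete. The FAS observed-case rate then moves toward a completer rate. The study plans no hypothesis test, so this percentage and its exact confidence interval are the main efficacy result.

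**Working it through.** **The plan's own figure.** Protocol 9.1 gives lower 95% limits of 40% and 54% for 35 patients at healing rates of 58% and 72%. The Clopper-Pearson lower limit is the 2.5% quantile of Beta(x, n − x + 1).
- With x = 0.58 × 35 = 20.3 and x = 0.72 × 35 = 25.2, the limits are 40.2% and 54.3%, which agrees.
- With whole patients, 20/35 gives 39.4% and 25/35 gives 53.7%.

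The illustration below uses 25/35, the whole-patient count nearest the planned 72%.

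**Where the nearest-visit rule cuts.** On-treatment FCS is scheduled at Day 28 (Visit 4) and Day 56 (Visit 6).
- Midpoint of the FCS visits: (28 + 56)/2 = Day 42.
- SAP 2.5 refers to scheduled visits in general. If pick-up Visit 5 (Day 42) counts, the cut is (42 + 56)/2 = Day 49.

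**Effect on the primary rate.** Assumptions: 25 of 35 completers healed; k further dosed patients stopped early, unhealed, for progression or non-response. The documents give no dropout rate, so k is shown over a range. If none of the exit values is assigned to Week 8, the rate is 25/35 = 71.4% (95% CI 53.7 to 85.4) whatever k is. If all are kept as not healed, it is 25/(35 + k):

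| k | Share of FAS | Rate, failures kept | 95% CI | Difference from 71.4% |
|---|---|---|---|---|
| 2 | 2/37 = 5.4% | 25/37 = 67.6% | 50.2 to 82.0 | 3.9 points |
| 4 | 4/39 = 10.3% | 25/39 = 64.1% | 47.2 to 78.8 | 7.3 points |
| 6 | 6/41 = 14.6% | 25/41 = 61.0% | 44.5 to 75.8 | 10.5 points |

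Differences are taken before rounding.

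**What LOCF and WOCF recover (k = 4, before any rescue reclassification).**
- All four have an exit FCS: 25/39 = 64.1%, so the whole gap is recovered.
- One has no post-baseline FCS and is still omitted: 25/38 = 65.8%, leaving 1.7 points.
- One has a healed Week 4 grade and no exit FCS, and is counted as healed: 26/39 = 66.7%, leaving 2.6 points.
- One of each: 26/38 = 68.4%, leaving 4.3 points.

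**The opposite case.** Suppose three of the four stoppers had healed, left for unrelated reasons and have no Week 8 value. The true rate is (25 + 3)/39 = 71.8%.
- Observed-case: 25/35 = 71.4%, 0.4 points low.
- Counting only the one failure-driven stop as not healed: 25/36 = 69.4%, 2.4 points low.
- Counting every missing value as not healed: 25/39 = 64.1%, 7.7 points low.

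**The case against.** The strongest reply is that the more specific text already keeps the exit FCS at Week 8: the endpoint names Visit 6, Visit 6 is also the discontinuation visit, stoppers complete its procedures, and healing is recorded on the eCRF by visit. On that reading the bias is zero for every patient with an exit FCS. This stands as a reasonable reading, but SAP 2.5 does not say that the label overrides its timing rule.

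It is also fair that the FAS LOCF and WOCF tables would show most of the gap, so the 7.3 points are not hidden. The patients these tables mishandle should be few, because progression or non-response normally needs an eye examination to establish. The headline rate would still be the unadjusted one, and the plan would not explain why the tables differ.

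The affected group is narrow. Patients still at Grade 3 after 8 weeks are observed failures and are untouched, and the Deterioration or No Improvement rule in Protocol 3.3 applies at Week 8 and during follow-up. With all efficacy analyses labelled exploratory (SAP 2.10), observed-case analysis is a disclosed choice. But this choice loses information where the reason for stopping is itself treatment failure.

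A reader might also infer that the FTS table cannot reveal the effect, since Protocol 9.2 limits that set to patients who receive all 8 weeks. The documents do not support this. The SAP supersedes the protocol's statistical text (SAP 1), and SAP 2.6.4 defines the FTS by treatment through Visit 6, which carries the same double meaning. No claim is made about what the FTS table shows.

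**Conclusion.** The point holds in conditional form. No rule counts an early stop for progression or investigator-assessed non-response as not healed. SAP 2.5, read literally, can take such a patient's exit FCS out of Week 8 and the patient out of the primary FAS denominator. If so, the primary rate is biased upward, by 3.9, 7.3 or 10.5 points for 2, 4 or 6 early failures. These sizes rest on an assumed 25 of 35 completers healed and assumed numbers of stoppers, all unhealed and none mapped to Week 8.

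A reader might go further and conclude that the plan certainly excludes these failures. It does not: under the Visit 6 label the bias is zero for anyone with an exit FCS. Nor is there a type I error issue, as no test is planned. This is a cheap improvement to the main estimate, worth making because a stated rule can otherwise distort it.

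**What to change.** 1. **SAP 5.1:** in the FAS primary analysis, count as not healed any dosed patient who stopped before Week 8 for progression or investigator-assessed non-response. This also covers such patients when the exit FCS is missing.
2. **SAP 2.5:** state that an FCS from a premature-discontinuation Visit 6 is analysed as Visit 6/Week 8 and is not reassigned by the nearest-visit rule.
3. **Optional:** add one FAS sensitivity table, beside LOCF and WOCF, that counts any missing Week 8 value as not healed.

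The cost is two sentences and at most one table, with no new data. The reported rate may be slightly less favourable. Item 2 also lets an early exit grade stand for Week 8 in patients who leave for unrelated reasons, whichever way that grade points. The optional table can understate healing when stops are unrelated to the eye (7.7 points in the opposite case above), so it should remain a sensitivity analysis.

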Appendix 2 Shells for Tables, Listing, and Figures List of tables

| Table Number | Table Title | Analysis Population |
|-----------------|--|------------------------|
| 14.1.1 | Analysis Populations | Screened |
| 14.1.2 | Subject Disposition | Screened |
| 14.1.3 | Visit Participation | Full Analysis Set |
| 14.1.4 | Demographics | Full Analysis Set |
| 14.1.5.1 | Medical History | Full Analysis Set |
| 14.1.5.2 | Ocular History | Full Analysis Set |
| 14.1.6.1.1 | Ocular Prior Medications | Full Analysis Set |
| 14.1.6.1.2 | Non-ocular Prior Medications | Full Analysis Set |
| 14.1.6.2.1 | Ocular Concomitant Medications | Full Analysis Set |
| 14.1.6.2.2 | Non-ocular Concomitant Medications | Full Analysis Set |
| 14.1.7.1 | Treatment Exposure of Study Product | Full Analysis Set |
| 14.1.7.2 | Washout Use of Artificial Tears | Full Analysis Set |
| 14.1.7.3 | Treatment Compliance of Study Product | Full Analysis Set |
| 14.2.1.1.1 | Percentage of Patients who Experienced with Epithelial Healing at 8 weeks | Full Analysis Set |
| 14.2.1.1.2 | Percentage of Patients who Experienced with Epithelial Healing at 8 weeks | Full Treated Set |
| 14.2.1.1.3 | Percentage of Patients who Experienced with Epithelial Healing at 8 weeks - LOCF | Full Analysis Set |
| 14.2.1.1.4 | Percentage of Patients who Experienced with Epithelial Healing at 8 weeks - WOCF | Full Analysis Set |
| 14.2.1.2 | Percentage of Patients who Achieved Epithelial Healing at Week 8 and Remained Healed during Follow-up | Full Treated Set |
| 14.2.1.3 | Percentage of Patients who Experienced with Epithelial Healing at 4 weeks | Full Analysis Set |
| 14.2.2.1 | Percentage of Patients who Experienced with Complete Healing at 8 weeks | Full Analysis Set |
| 14.2.2.2 | Percentage of Patients who Achieved Complete Healing at Week 8 and Remained Healed during Follow-up | Full Treated Set |
| 14.2.2.3 | Percentage of Patients who Experienced with Complete Healing at 4 weeks | Full Analysis Set |
| 14.2.3.1 | Corneal Sensitivity Change from Baseline to Weeks 4, 8, and 32 | Full Analysis Set |
| 14.2.3.2 | Percentage of Patients Improved from Baseline in Corneal Sensitivity at 4, 8 and 32 weeks | Full Analysis Set |
| 14.2.4 | Schirmer I Change from Baseline to Weeks 4, 8, and 32 | Full Analysis Set |
| 14.2.5 | TFBUT Change from Baseline to Weeks 4, 8, and 32 | Full Analysis Set |
| 14.2.6.1 | BCDVA Change from Baseline to Weeks 4, 8, and 32 | Full Analysis Set |

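### On scheduled visits the planned WOCF analysis reduces to LOCF and is joined to rescue-as-failure, so the two tables test one missing-data assumption and cannot separate rescue use from missing data

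*SAP*

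**What the plan says.** SAP 5.1 makes epithelial healing at Week 8 the primary efficacy variable: "The primary analysis will be based on observed cases (i.e. no missing data imputation"). For the first sensitivity analysis, "the last post baseline observation prior to Week 8 will be carried forward for imputing missing data at Week 8" (LOCF). A further sentence uses the worst post-baseline observation before Week 8 instead (WOCF) and, in the same sentence, adds that "patients who took any rescue medication prior to Week 8 will be considered as a treatment failure".

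The table list in SAP Appendix 2 gives each analysis one table in the full analysis set (FAS): 14.2.1.1.3 for LOCF, and 14.2.1.1.4, titled "Percentage of Patients who Experienced with Epithelial Healing at 8 weeks - WOCF". It lists no table for rescue-as-failure alone and none that counts missing Week 8 data as not healed.

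Under SAP 1.3.3.1 the staining grade "will be determined at Visit 1, 2, 4, 6, 7 using the NEI" scale. The protocol's schedule of evaluations agrees: Visits 3 and 5 are product pick-up visits without staining.

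Two provisions can add a grade. SAP 2.5 says: "Post first dose unscheduled assessments will be taken into account for worst-case determination as applicable". Protocol 6.2 requires the Visit 6 procedures, which include staining (Protocol 6.1.6), when a patient discontinues prematurely.

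**The concern.** SAP 2.11 promises sensitivity analyses under several imputation approaches. A reader who sees an LOCF table and a WOCF table will expect two different assumptions about the missing grades, the second harsher than the first. If the tables agree, that reader will conclude that the healing rate is robust to dropout. If WOCF is lower, the reader will blame the missing data.

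Neither inference is safe. With one scheduled grade before Week 8, agreement is largely a product of the visit schedule. The rescue rule also reclassifies patients whose Week 8 grade is present, so it can lower the WOCF figure when nothing is missing at all. Rescue use is foreseeable: SAP 1.3.2.2 allows artificial tears up to four times per day at the investigator's discretion.

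The group for whom the assumption matters may not be small. Patients who stop before completing 8 weeks are replaced (Protocol 6.2), so the FAS can exceed the 35 evaluable patients. The documents do not say by how many.

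**Working it through.** **1. The plan's own figure, used as the base case.** Protocol 9.1 gives 35 evaluable patients, healing of 58% at Week 4 and 72% at Week 8, and lower 95% limits of 40% and 54%. The exact (Clopper-Pearson) lower limit is the 2.5% quantile of Beta(x, n − x + 1).
- Week 4: x = 35 × 0.58 = 20.3 gives 40.2%.
- Week 8: x = 35 × 0.72 = 25.2 gives 54.3%.

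Both figures are reproduced. The nearest whole count at Week 8 is 25/35 = 71.4% (exact 95% CI 53.7 to 85.4).

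**2. Last against worst.** Grades run from 0 to 3, and healed means grade 0 or 1.
- One grade before Week 8 (Visit 4 only): last equals worst for all 4 possible grades.
- Two grades: there are 4 × 4 = 16 sequences. The carried grade differs in 6, and healed status differs in 4: (2,0), (2,1), (3,0) and (3,1). In each, LOCF says healed and WOCF says not healed.

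These are counts of possible sequences, not probabilities.

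**3. Missing data.** Assumed inputs: 25 of 35 completers healed; m further FAS patients without a Week 8 grade, each with one Visit 4 grade; k of them healed at Visit 4, with k = 0.58 × m rounded; no rescue.
- Observed cases = 25/35
- LOCF = WOCF = (25 + k)/(35 + m)
- Missing-as-failure = 25/(35 + m)

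| m | k | Observed | LOCF = WOCF (95% CI) | Missing-as-failure (95% CI) |
|---|---|---|---|---|
| 2 | 1 | 71.4% | 26/37 = 70.3% (53.0–84.1) | 25/37 = 67.6% (50.2–82.0) |
| 4 | 2 | 71.4% | 27/39 = 69.2% (52.4–83.0) | 25/39 = 64.1% (47.2–78.8) |
| 6 | 3 | 71.4% | 28/41 = 68.3% (51.9–81.9) | 25/41 = 61.0% (44.5–75.8) |
| 8 | 5 | 71.4% | 30/43 = 69.8% (53.9–82.8) | 25/43 = 58.1% (42.1–73.0) |

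The direction of the LOCF shift depends on the assumption. If 5 patients lack Week 8, 2 of them healed at Visit 4 and 3 with no post-baseline grade, LOCF = WOCF = 27/37 = 73.0%, above observed cases, while missing-as-failure is 25/40 = 62.5%. The 3 ungraded patients are in neither the numerator nor the denominator of the carried-forward results.

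**4. The rescue rule alone.** With nothing missing and r healed rescue users set to failure, the rate is (25 − r)/35:
- r = 2: 23/35 = 65.7%
- r = 4: 21/35 = 60.0%
- r = 6: 19/35 = 54.3%

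**5. Both together.** With m = 4, LOCF is 27/39 = 69.2%, and WOCF without the rescue rule is also 27/39. With 3 healed rescue users set to failure, the WOCF table shows 24/39 = 61.5%. The whole gap of 69.2 − 61.5 = 7.7 points is rescue, under a title that names only the imputation.

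**The case against.** A reader might infer that the planned analyses do not test missing data at all. The documents do not support that: LOCF fills missing Week 8 grades and changes both the numerator and the denominator, as step 3 shows.

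A reader might also infer that WOCF always equals LOCF. That is too strong as well. A patient who stops after Visit 4 should have an exit staining grade, and unscheduled assessments can enter the worst-case value. Either can make last and worst differ. An exit grade may also be assigned to Week 8 under the nearest-visit rule in SAP 2.5, in which case nothing is missing. The exit visit also shrinks the group with no post-baseline grade, mainly to patients with neither a Visit 4 nor an exit assessment, such as some of those lost to follow-up.

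Further points on that side are fair:
- The WOCF sentence could be read as two analyses.
- The appendix shows table titles only, and SAP 1 says the mock shells are a separate working document, so explanatory footnotes cannot be ruled out.
- The planned listings of staining and artificial-tear use may let a reader separate the effects patient by patient.
- Combining WOCF with rescue-as-failure is a coherent pessimistic scenario.
- The study is single-arm, has no hypothesis test (Protocol 9.3.2), and treats all efficacy analyses as exploratory (SAP 2.10).

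These points limit the finding but do not remove it. The table list supports reading the sentence as one combined analysis. The exit visit helps only if it takes place, and no rule says how its grade is used. Listings do not replace a summary rate with an interval.

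**Conclusion.** The point holds in limited form. On scheduled visits WOCF adds nothing to LOCF, and a difference between Tables 14.2.1.1.3 and 14.2.1.1.4 would mainly reflect rescue use. The two analyses amount to essentially one missing-data assumption, that the earlier status persists. Patients with no post-baseline grade are left out of both, and no planned analysis counts a patient with missing Week 8 data as not healed.

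In the tabulated scenarios the carried-forward rate stays within about 3 points of observed cases (71.4 − 68.3 = 3.1). Missing-as-failure falls by 3.8 points with 2 missing (71.4 − 67.6) and by 13.3 with 8 (71.4 − 58.1). The rescue rule alone costs 5.7 points with 2 healed rescue users (71.4 − 65.7) and 17.1 with 6 (71.4 − 54.3). All of these rest on assumed numbers missing and rescued, and on the protocol's 58% Week 4 rate applying to patients who lack Week 8.

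The consequence is for interpretation. The primary observed-case result is unchanged and no error rate is at stake. This is a cheap improvement, not a flaw that undermines the study.

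**What to change.** In SAP 5.1 and the table list:

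1. Report rescue-as-failure on observed cases in its own FAS table, and show the number of patients reclassified.
2. Add an FAS analysis that counts every patient without a Week 8 grade as not healed, including those with no post-baseline grade. It can replace WOCF, or stand beside it with the rescue rule removed from the WOCF table.
3. State whether a staining grade taken at a discontinuation visit counts as the Week 8 grade. If it does not, say whether it may be carried forward.
4. Make each table title or footnote name the rule applied and give the number of grades imputed.

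The cost is one extra table if missing-as-failure replaces WOCF, or two if WOCF is kept. No new data are needed and patient care does not change. The price is a sensitivity rate that may be less favourable, by the amounts shown above if dropout or rescue use is appreciable.
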